**Recommended LCM dose titration for subjects enrolling directly into SP848**

Formulation	Week 1	Week 2	Week 3	Week 4	Week 5	Week 6
Oral solution (syrup)	2mg/kg/day (1mg/kg bid)	4mg/kg/day (2mg/kg bid)	6mg/kg/day (3mg/kg bid)	8mg/kg/day (4mg/kg bid)	10mg/kg/day (5mg/kg bid)	12mg/kg/day (6mg/kg bid)
Tablet	100mg/day (50mg bid)	200mg/day (100mg bid)	300mg/day (150mg bid)	400mg/day (200mg bid)	500mg/day (250mg bid)	600mg/day (300mg bid)

bid=twice daily; LCM=lacosamide

**4.4.1.3 All subjects**

The investigator, together with the subject/caregiver (including parent/legal guardian), will be able to choose either the oral solution (syrup) formulation or the tablet formulation of LCM in this study. The study medication will be orally administered bid (at 12-hour intervals, once in the morning and once in the evening) in equally divided doses. The oral solution (syrup) formulation will be measured and orally administered via a dosing syringe. The selection of doses, titration scheme, and rate of taper in SP847 were based on adult studies and were adjusted to a mg/kg basis plus 40% (ie, 600mg/day adult dose of LCM corresponds to  $[600\text{mg}/70\text{kg}] \times 1.4 =$  approximately 12mg/kg/day for a child). The selection of doses in this trial is based on the maximum recommended dose in SP847.

The investigator may adjust the LCM dose to a minimum of 2mg/kg/day (oral solution [syrup]) or 100mg/day (tablet) and a maximum of 12mg/kg/day (oral solution [syrup] or the corresponding dose levels for the tablet formulation) not to exceed 600mg/day based on body weight, even if the subject's body weight exceeds 50kg. The maximum permitted LCM dose in SP848 is 12mg/kg/day or 600mg/day, whichever is lower.

The investigator may increase the dose of LCM no faster than 2mg/kg/day (oral solution [syrup]) or 100mg/day (tablet) per week to a maximum of 12mg/kg/day (oral solution [syrup] or the corresponding dose levels for the tablet formulation) not to exceed 600mg/day based on body weight, even if the subject's body weight exceeds 50kg. The maximum permitted LCM dose in SP848 is 12mg/kg/day or 600mg/day, whichever is lower. The investigator may decrease the dose of LCM to a minimum of 2mg/kg/day (oral solution [syrup] or the corresponding dose level for the tablet formulation). Increases in the LCM dose must occur only during office visits. It should be noted, in cases of incomplete doses (eg, subject spits out all or a portion of the syrup), missed doses, or administration of an erroneous volume of syrup, study medication should not be readministered and these subjects would remain at their assigned dose.

Subjects enrolling from SP847 will have the option of remaining on the oral solution formulation of LCM or switching to the commercial tablet formulation, if feasible. Consideration of the current LCM milligram dose in the oral solution (syrup) should occur if/when transitioning to the tablet formulation. In cases where the LCM dose received with the oral solution (syrup) is not supported by the tablet strengths available in SP848 (50mg and 100mg), a clinical decision must

be made by the investigator or other study physician to either increase or decrease the LCM dose to the next multiple of 100mg with a maximum permitted dose of 600mg/day.

Subjects achieving a dose of LCM  $\geq$ 6mg/kg/day (oral solution [syrup]) or  $\geq$ 300mg/day (tablet) who withdraw during the study should taper off study medication. It is recommended that the dose be tapered gradually in weekly decrements of 4mg/kg/day (oral solution [syrup]) or 200mg/day (tablet) (see tables below). A slower taper of 2mg/kg/day (oral solution [syrup]) or 100mg/day (tablet) is permitted, if medically necessary. In case of an emergency, a faster taper is permitted after discussion with the medical monitor, whenever possible.

#### **Recommended LCM dose reduction (taper) for oral solution (syrup) formulation**

Maximum LCM dose achieved a	Taper schedule		
	Week 1	Week 2	Week 3
12mg/kg/day (6mg/kg bid)	8mg/kg/day (4mg/kg bid)	4mg/kg/day (2mg/kg bid)	0
10mg/kg/day (5mg/kg bid)	6mg/kg/day (3mg/kg bid)	2mg/kg/day (1mg/kg bid)	0
8mg/kg/day (4mg/kg bid)	4mg/kg/day (2mg/kg bid)	0	–
6mg/kg/day (3mg/kg bid)	2mg/kg/day (1mg/kg bid)	0	–
4mg/kg/day (2mg/kg bid)	0	–	–

bid=twice daily; LCM=lacosamide

a Maximum LCM dose achieved is based upon the maximum recommended dose in SP847.

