### 5.3 Visit 1 (Week 0)

For subjects who completed SP847, Visit 1 for SP848 was the same as Day 2 of the second PK collection time period (which may include an overnight stay at a hospital or medical facility) in SP847 (Day 28 for Cohorts 1, 2, 3, and 5 with maximum recommended dose of 8mg/kg/day; Day 35 for Cohorts 2 to 5 with maximum recommended dose of 10mg/kg/day; and Day 42 for Cohorts 2 to 5 with maximum recommended dose of 12mg/kg/day). For subjects who discontinued SP847 due to a dose reduction or status epilepticus, Visit 1 was the Early Termination Visit in SP847. For subjects in SP847 who were titrated up to the maximum permitted dose of 600mg/day sooner than the study schedule would ordinarily indicate (based on body weight) and who enroll in SP848, the Early Termination Visit of SP847 also served as Visit 1 for SP848.

For subjects who enroll in SP848 after participation in other LCM pediatric clinical studies besides SP847 (ie, SP0966 and EP0060) in epilepsy, SP848 Visit 1 will be specified in the respective primary study protocol.

For subjects who enter directly into SP848 (without prior participation in SP847 or other LCM pediatric clinic studies in epilepsy), the LCM dose will be titrated at weekly intervals as described in Section 4.4.1.2 and Section 5.2. These subjects will reach Visit 1 either (1) when the LCM dose is titrated to a level that, in the opinion of the investigator, optimizes tolerability and seizure control, or (2) when the maximum permitted LCM dose is reached (12mg/kg/day [or 600mg/day based on body weight, whichever is lower]). In the case of a subject who requires a dose reduction during the Titration Visits, the subject's LCM dose will be returned to the

previous dose level and the next clinic visit will be Visit 1 at the reduced level. Visit 1 should occur at least 5 days after the final TV. At Visit 1, the progress in SP848 for subjects who entered directly into SP848 and for subjects who have enrolled from SP847 or other LCM pediatric clinical studies in epilepsy will be aligned; subsequent regularly scheduled clinic visits for all subjects will be at 4-week intervals as outlined in the following sections.

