#### **5.4 Telephone contacts (Weeks 2, 6, 10, 16, 24, 32, 40, 48, 66, and 78)**

Between scheduled clinic visits, the investigator (or designee) should contact the subject's caregiver (including parent/legal guardian) by telephone. The investigator (or designee) should remind the subject's caregiver (including parent/legal guardian) to ensure the diary is completed and to bring unused LCM to the next clinic visit. The following should be performed via telephone:

- Concomitant medications assessment
- Concomitant AEDs assessment
- Adverse event reporting

If an AE necessitates the subject's withdrawal from the study, the subject should return for an Early Termination Visit ([Section 5.17](#)) as soon as possible.

Lacosamide is supplied so that the subject or caregiver (including parent/legal guardian) can immediately decrease their dose, if needed, in consultation over the telephone with the investigator or subinvestigator. Thus, LCM can be continued at a decreased dose until a clinic visit can be scheduled.

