## 5.18 Unscheduled Visit(s)

An Unscheduled Visit may be performed at the investigator's discretion. If the LCM dose is decreased between scheduled clinic visits due to an AE, if an LCM dose increase is required at any time, or if a new concomitant AED is introduced, the subject must return for an Unscheduled Visit. If an AE prompts a dose reduction, the reduction can be implemented immediately at the investigator's discretion. However, the subject should return to the clinic as soon as possible for an Unscheduled Visit.

The following assessments are required:

- Concomitant medications assessment
- Concomitant AEDs assessment
- Brief physical examination
- Brief neurological examination

- 12-lead ECG (2 interpretable recordings approximately 20 to 30 minutes apart prior to vital signs assessment and collection of any blood samples)
- Vital signs assessment (blood pressure and pulse)
- Body weight
- LCM return/compliance (as applicable)
- Subject diary assessment
- C-SSRS (only if Unscheduled Visit is conducted due to an AE)
- Adverse event reporting
- Health care resource use
- Dispense LCM (as applicable)
- If possible, a blood sample for LCM and concomitant AED plasma concentrations (at any time post-dosing with LCM) if the unscheduled visit is due to a SAE

Additional assessments can be performed at the investigator's discretion.

All subjects will be required to have an ECG (2 interpretable recordings) conducted at LCM  $C_{max}$  1 week after an initial LCM dose increase to a LCM dose level that is  $\geq 8\text{mg/kg/day}$  or after a new concomitant AED is introduced. This ECG can be conducted at an Unscheduled Visit, if necessary. Subjects having a LCM dose increase to  $\geq 8\text{mg/kg/day}$  will be required to arrive at the clinic prior to taking their morning dose of LCM. Subjects will be administered their morning LCM dose by study personnel at the clinic so that an ECG (2 interpretable recordings approximately 20 to 30 minutes apart prior to vital signs assessment) can be performed 30 minutes to 1 hour after the administration of LCM (ie, at LCM steady state  $C_{max}$ ).

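### Both taper tables are entered by the maximum dose ever achieved, so after a large earlier dose cut the Week 1 taper dose is an increase

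*Protocol*

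**What the plan says.** Section 4.4.1.3 states the rule in prose: "It is recommended that the dose be tapered gradually in weekly decrements of 4mg/kg/day (oral solution [syrup"), with 200mg/day as the tablet equivalent, and refers to the tables that follow. Subjects who achieved at least 6mg/kg/day or 300mg/day and who withdraw should taper. A slower taper of 2mg/kg/day or 100mg/day is permitted if medically necessary.

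The first column of both tables is the maximum LCM dose achieved, and each carries the footnote "Maximum LCM dose achieved is based upon the maximum recommended dose in SP847". Nothing in the protocol says to enter the tables at the current dose.

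The protocol also lets the dose fall before taper:

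- Section 4.4.1.3: "The investigator may decrease the dose of LCM to a minimum of 2mg/kg/day" (or the corresponding tablet dose), with no limit on the size of a reduction.
- Section 5.4: the subject or caregiver "can immediately decrease their dose, if needed, in consultation over the telephone with the investigator or subinvestigator".
- Section 5.18: "If an AE prompts a dose reduction, the reduction can be implemented immediately".

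Increases are restricted. Section 4.4.1.3 says "The investigator may increase the dose of LCM no faster than 2mg/kg/day (oral solution [syrup") or 100mg/day (tablet) per week, and "Increases in the LCM dose must occur only during office visits".

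**The concern.** Table and prose agree only when the child starts taper from the highest dose ever taken. A child whose dose was cut earlier, for example for an adverse event, no longer meets that condition, and intolerable adverse events are also the first mandatory withdrawal reason in Section 4.3.3. A cut before taper is therefore foreseeable.

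The historical reading of the heading is a natural one. The criterion for taper, and for dispensing taper drug in Sections 5.16 and 5.17, is itself the dose achieved. A child who once reached 12mg/kg/day and now takes 4 is sent to taper, and the only row that fits the heading is the 12mg/kg/day row. The footnote does not help, since it refers to SP847, a study that directly enrolled subjects never entered.

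At stake is a dosing instruction for children stopping an antiepileptic drug. No study variable or analysis is involved.

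**Working it through.** **Inputs.** Week 1 doses come from the two taper tables. The taper step (4mg/kg/day or 200mg/day), the minimum dose (2mg/kg/day or 100mg/day) and the limit on increases (2mg/kg/day or 100mg/day per week) come from the text of Section 4.4.1.3. Dose levels are taken in steps of 2mg/kg/day or 100mg/day.

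**Reproducing the tables.** With dose in week k = max(0, row dose − k × step), the syrup rows 12, 10, 8, 6, 4 give Week 1 doses of 8, 6, 4, 2, 0mg/kg/day, and the tablet rows 600, 500, 400, 300, 200 give 400, 300, 200, 100, 0mg/day. All ten rows, including the later weeks, match. The table arithmetic is right; the row label is the issue.

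**When the literal reading fails.** Read by the heading, Week 1 = maximum − 4. The change from the dose being taken is

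Week 1 − current = (maximum − current) − 4.

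This is positive exactly when the earlier cut exceeded 4mg/kg/day and zero when it equalled 4mg/kg/day. For tablets the threshold is 200mg/day.

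**Every syrup combination** (change from current dose in Week 1, mg/kg/day):

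| Maximum achieved | Week 1 in table | Current 12 | 10 | 8 | 6 | 4 | 2 |
|---|---|---|---|---|---|---|---|
| 12 | 8 | −4 | −2 | 0 | +2 | +4 | +6 |
| 10 | 6 | | −4 | −2 | 0 | +2 | +4 |
| 8 | 4 | | | −4 | −2 | 0 | +2 |
| 6 | 2 | | | | −4 | −2 | 0 |
| 4 | 0 | | | | | −4 | −2 |

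- All combinations: 6 + 5 + 4 + 3 + 2 = 20, of which 6 are increases, 4 unchanged and 10 reductions.
- Current dose below maximum: 20 − 5 = 15, of which 6 are increases, 4 unchanged and 5 reductions.
- Increases above the weekly limit of 2mg/kg/day: three (12/4, 12/2 and 10/2, written as maximum/current).

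**Tablets.** The counts are the same. The increases are 600/300 (+100), 600/200 (+200), 600/100 (+300), 500/200 (+100), 500/100 (+200) and 400/100 (+100mg/day). Three exceed 100mg/day: 600/200, 600/100 and 500/100.

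**The reduction foreseen in titration.** Section 5.3 returns the subject to the "previous dose level and the next clinic visit will be Visit 1 at the reduced level". That is normally one 2mg/kg/day step, and a one-level cut gives −2 in all five rows, so this route does not produce an increase.

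**With the rows read as the dose at taper start.** Week 1 − row dose = −4mg/kg/day in 5 of 5 syrup rows and −200mg/day in 5 of 5 tablet rows. For a maximum of 12 and a current dose of 6, Week 1 becomes 2 instead of 8mg/kg/day; for a current dose of 4 it becomes 0 instead of 8.

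**The case against.** The strongest reply is that the text the tables serve excludes the harmful reading. The prose calls for decrements, both tables are titled as dose reductions, and the decrement rule is repeated without a table in Sections 1, 4.1.1, 5.16 and 5.17. An increase is not a taper, so most clinicians would step down from the current dose. The schedule is only recommended, and Section 4.3.3 asks for discussion with the medical monitor whenever possible. The word achieved is also used loosely: Section 1 uses it for the SP847 dose on which subjects begin this study, while Section 4.1.1 describes the same starting dose as the one last received. The breach of the limit on increases is arguably not a second defect but further evidence that no increase was intended.

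Most of this stands, and it is why the point is minor. It does not remove the mismatch. The word maximum rules out reading the heading as the current dose, and no sentence redirects the reader. The office-visit rule is not a reliable barrier, because taper drug is dispensed at Visit 13 and the Early Termination Visit. Section 5.21 also provides for tapering instructions to a subject who cannot attend the clinic.

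A further objection is that, under the relabelled table, a child who once reached 6mg/kg/day or more and now takes 4 goes straight to 0. That is true, but the prose decrement already gives the same result, and the slower taper remains available if medically necessary.

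**Conclusion.** The concern holds as a minor drafting error in a paediatric dosing table: the row label conflicts with the rule the table is meant to apply. The conflict needs an earlier cut of at least one full taper step. An increase needs a cut of more than 4mg/kg/day or 200mg/day, which is possible only in the top three rows of each table (12, 10 and 8mg/kg/day; 600, 500 and 400mg/day).

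The count of 6 in 20 assumes the regular dose levels above and weights all combinations equally. How many children would stop after such a cut is not given, so no frequency can be stated. The practical risk is small. The threshold for taper and for dispensing, which is also based on the dose achieved, is not in question.

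**What to change.** In both tables of Section 4.4.1.3, change the first column heading to *LCM dose at start of taper* and delete the SP847 footnote, which has no purpose under that heading. The doses in the tables stay as they are. No row is needed for a current dose of 2mg/kg/day or 100mg/day, because either permitted decrement takes it to 0.

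Leave the threshold of at least 6mg/kg/day or 300mg/day achieved, and the slower taper option, unchanged, so that no child loses access to taper drug.

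The cost is one heading and one footnote in each of two tables at the next amendment. Visits, data collection, drug supply and dispensing rules are untouched.

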#### **Recommended LCM dose reduction (taper) for tablet formulation**

Maximum LCM dose achieved a	Taper schedule		
	Week 1	Week 2	Week 3
600mg/day (300mg bid)	400mg/day (200mg bid)	200mg/day (100mg bid)	0
500mg/day (250mg bid)	300mg/day (150mg bid)	100mg/day (50mg bid)	0
400mg/day (200mg bid)	200mg/day (100mg bid)	0	–
300mg/day (150mg bid)	100mg/day (50mg bid)	0	–
200mg/day (100mg bid)	0	–	–

bid=twice daily; LCM=lacosamide

a Maximum LCM dose achieved is based upon the maximum recommended dose in SP847.

#### 4.4.1.4 Study completion

At the completion of the study, investigators should discuss treatment options with the subject and/or their parent/legal guardian to best manage the subject's epilepsy. Taper of LCM may not be required for some subjects who complete the study depending on the treatment option selected by the investigator in consultation with the subject and/or parent/legal guardian. These subjects should complete Visit 13/Termination Visit and then complete the Safety Follow-Up telephone contact 28 to 35 days after Visit 13/Termination Visit. The Final Visit is not required for subjects who complete the study and who do not undergo taper of LCM. The Safety Follow-Up Visit and the Safety Follow-Up telephone contact are not required for subjects who participate in EP0151 or EP0152.

Subjects who complete the study and discontinue use of LCM (as determined by the investigator in consultation with the subject and/or parent/legal guardian) should taper LCM gradually as described in Section 4.4.1.3. These subjects should complete Visit 13/Termination Visit, followed by the Final Visit which occurs 2 weeks after the final dose of study medication, and then the Safety Follow-Up telephone contact which occurs 28 to 35 days after the last dose of LCM.

#### 4.4.2 Description of investigational medicinal product

Beginning with protocol Amendment 3, the oral solution formulation contains 10mg/mL of drug substance (formerly containing 15mg/mL of drug substance) and is colorless to pale yellow in appearance. The oral solution (syrup) will be packaged in amber polyethylene terephthalate (PET) bottles with a white, child-proof, polypropylene screw cap.

The tablet formulation will be supplied in doses of 50mg and 100mg. The 50mg tablets are light pink, oval, film-coated tablets debossed with "SP" on 1 side and "50" on the other. The 100mg tablets are dark yellow, oval, film-coated tablets debossed with "SP" on one side and "100" on the other. The tablets will be packaged in high-density polyethylene bottles with a child-proof, polypropylene screw cap.

#### 4.4.3 Randomization

This is an open-label study; subjects will not be randomized. Subjects who participated in SP847 or other LCM pediatric clinical studies in epilepsy will keep the unique number assigned in the primary study.

Subjects enrolling directly into SP848 without participation in a previous LCM clinical study will be assigned unique numbers for the purpose of study and subject identification, as well as for subject confidentiality. At the Screening Visit, each subject will be assigned the unique identifying number for this study.

#### 4.5 Expected duration of the study

The maximum duration of LCM administration for an individual subject will be approximately 2 years or until approval of the marketing application (for Japan only), whichever comes first.

The start of the study is defined as the first visit of the first subject entering the study. The end of the study is defined as the date of the last visit of the last subject in the study.

#### **4.6 Concomitant medication(s)/treatment(s)**

The following medications/therapies are prohibited during the course of this study:

- Monoamine oxidase inhibitor-A compounds
- Narcotic analgesics
- Cannabidiols not approved or indicated for epilepsy by a local health authority

All concomitant medications and treatments must be recorded in the appropriate study documents (eCRF and source document).

Stable use of amphetamines and sedative antihistamines is allowed during the study. Also, stable, low doses of anxiolytics or hypnotics (ie, diazepam 5mg/day) are allowed for nonepilepsy indications only.

Therapy that becomes necessary, in the investigator's opinion, during the course of the study must not be refused to a subject, even if described above as a therapy that is expressly not permitted. The subject's participation in this study may be discontinued in such a case.

#### **4.7 Procedures for monitoring subject compliance**

Subjects' caregivers (including parent/legal guardian) will be instructed to return unused medication at each study visit. Returned medication will be reconciled by the investigator (or designee) in order to monitor the subject's compliance with the medication schedule. Drug accountability must be done in the subject's/caregiver's presence in order to obtain explanations regarding discrepancies in compliance with the dosing regimen.

All findings will be documented on forms provided by UCB BIOSCIENCES. Subject's noncompliance with regards to intake of LCM is defined as being less than 75% or more than 125% compliant with the dosage schedule.

If a subject is found to be noncompliant, a decision will be made by the investigator, in conjunction with UCB BIOSCIENCES, as to whether the subject should be withdrawn from the study.

### **5 TREATMENT PROCEDURES BY VISIT**

For all scheduled visits and telephone contacts (with the exception of the Safety Follow-Up telephone contact), a visit window of  $\pm 7$  days relative to Visit 1 is applicable. The Safety Follow-Up telephone contact will be performed 28-35 days after the last dose of LCM. The Safety Follow-Up Visit and the Safety Follow-Up telephone contact are not required for subjects who participate in EP0151 or EP0152.

Assessments will be done during monthly visits for the first 3 months, every 2 months for the remainder of Year 1, and every 3 months for Year 2. A detailed tabular schedule of study procedures is provided in [Section 16.1](#). For further details of the assessments and the required procedures and methods, please refer to [Section 6](#), [Section 7](#), and [Section 8](#).

## 5.1 Screening Visit

Beginning with Protocol Amendment 4, at selected sites, up to approximately 100 eligible pediatric subjects  $\geq 4$  years to  $\leq 17$  years of age who have not previously participated in a LCM clinical study will be permitted to enroll directly into SP848.

At the Screening Visit, subjects entering directly into SP848 (ie, subjects who have not participated in SP847 or another applicable LCM pediatric clinical study in epilepsy) will be evaluated for their suitability for enrollment in SP848. The Screening Visit is not applicable for subjects who have participated in SP847 or another applicable LCM pediatric clinical study in epilepsy; the first visit in SP848 for these subjects is Visit 1 (see Section 5.3).

The Screening assessments will be conducted up to 14 days prior to the first administration of LCM. It is acceptable for the Screening assessments to be conducted on more than 1 day, although it should not be done over longer than 1 week. Prior to the conduct of any study-related procedures, a complete explanation (both verbally and written) of the nature and purpose of the study will be given to the subject (when possible or as required according to local IRBs/IECs) and the subject's parent/legal guardian by the investigator (or designee). The subject's parent/legal guardian will be requested to sign and date the IRB/IEC-approved Informed Consent Form. When possible, or as required by the local IRB/IEC, the subject will be requested to give assent to participate in the study. Each subject's eligibility for the study will be determined on the basis of the inclusion/exclusion criteria and the results of the following pretreatment assessments (for further details of the assessments and the required procedures and methods, please refer to Section 6, Section 7, and Section 8 of this protocol).

- Concomitant medications assessment
- Concomitant AEDs assessment
- Medical history assessment
- Seizure history over the past 4 weeks (historical Baseline)
- Complete physical examination
- Complete neurological examination
- 12-lead ECG (2 interpretable recordings approximately 20 to 30 minutes apart prior to vital signs assessment and collection of blood sample)
- Vital signs assessment (blood pressure and pulse)
- Body weight assessment
- Height assessment
- Blood sample for clinical chemistry, hematology, and endocrinology
- Urine sample for urinalysis
- Serum pregnancy test for female subjects of childbearing potential
- Tanner Stage assessment (if applicable)
- C-SSRS

- Achenbach CBCL to be completed by the parent(s)/legal representative(s) (CBCL/1½-5 for children from 18 months to 5 years 11 months and CBCL/6-18 for children 6 years and older)
- Bayley-III scales for children <18 months of age enrolled in English-speaking countries
- BRIEF-P/BRIEF score (if applicable)
- PedsQL score (if applicable)
- Adverse event reporting
- Health care resource use
- Dispense subject diary

The subject will be scheduled to return for a clinic visit (TV) less than 14 days from the last Screening Visit assessment(s).

